Baseline questionnaires to be administered during the first two weeks will include:

- The FIT-60 (Flexibility Index Test), a standard measure of traits associated with mindfulness (Batink et al., 2016), such as "I observe my feelings without losing myself in them" and "It is OK if I remember something unpleasant," and (reverse scored) "I believe that some of my thoughts are abnormal or bad and that I shouldn't think like that." We will readminister this at week 11 to test the hypothesis that mindfulness scores will increase more in participants randomized to the JITAI intervention group than in participants randomized to the EMA group.
- The DTCQ (Drug-Taking Confidence Questionnaire) (Sklar & Turner, 1999), an 8-item measure of coping self-efficacy in the context of resisting lapses to drug misuse. We will readminister this at week 11 to test the hypothesis that scores will increase more in participants randomized to the JITAI intervention group than in participants randomized to the EMA group.
- The COPE (Carver et al., 1989), a theory-based, empirically validated 60-item questionnaire assessing both general coping styles and coping behaviors in specific situations. We will use this to test whether preferred coping styles are

[figure not shown]
associated with differences in momentary responsiveness to CBT-based vs. ACT-based messages. We will also readminister it at week 11 to test the hypothesis that participants randomized to the JITAI group will begin to adopt a broader range of coping styles than those randomized to the EMA group.

- The Monetary-Choice Questionnaire (MCQ) (Kirby et al., 1999), a 27-item assessment of discounting of future rewards. We will administer this at baseline to test whether people with steep discounting functions are initially resistant to ACT. We will also readminister it at week 11 to test whether participants randomized to the JITAI group will begin to show less discounting.
- The Need for Closure scale (Kruglanski et al., 2013), a 47-item assessment of dislike for ambiguity and uncertainty. We will administer this at baseline to test whether high scorers benefit more from CBT messages than from ACT messages. We will also readminister it at week 11 to test whether participants randomized to the JITAI group (all of whom will be exposed to ACT) will begin to show less need for closure.

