2. Analysis of study outcomes

Hypothesis 1, proximal: Main effect of messaging (delivery of either a CBT-based or ACT-based message will increase self-efficacy and decrease cravings and other negative states 20 minutes later, compared with the control message).

We will use multilevel random-intercept models (with data from the JITAI group only) to test the hypothesis of a proximal benefit of messages. The dependent variables, in separate models, will be participants' ratings of self-efficacy, craving, mood, and message helpfulness in EMA "post" assessments, controlling for the ratings in "pre" assessments. The main independent variable will be message type: active (CBT or ACT) versus none ("thank you" control condition). We will use an autoregressive error structure to account for within-person correlations. A significant beneficial effect on any of the outcome measures (self-efficacy, craving, mood, message helpfulness) will be taken as partial support for the hypothesis; significant beneficial effects on all the outcome measures will be taken as full support.

Hypothesis 2, proximal: Strategy-situation fit (the effects of the messages will be moderated by the circumstances in which they are provided).

The main analysis here (again, with data from the JITAI group only) will be a test of whether CBT messages are most effective in controllable situations and ACT messages are most effective in noncontrollable situations. We will categorize a situation as *noncontrollable* when a participant gives a response of less than 50/100 on either of these two "pre" items: (1) "I could easily be somewhere else right now if I wanted," (2) "I could easily get out of what I'm doing right now." Otherwise, we will categorize the situation as *controllable*. In the subset of instances in which an active message was given, multilevel models similar to those for hypothesis 1 will be run with the predictors Intervention Type (either CBT or ACT), controllability (y/n), and their interaction. A significant interaction (in the expected direction) on any of the outcome measures (self-efficacy, craving, mood, message helpfulness) will be taken as partial support for the hypothesis; significant beneficial effects on all the outcome measures will be taken as full support.

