Hypothesis 4, distal: Differential responses over time (CBT messages will be rated as helpful almost immediately; ACT messages may have to be lived with for several weeks, but may also stand up better to repetition).

In the JITAI participants, we will test this hypothesis with time-varying effect models (TVEMs) (Shiyko et al., 2012). These are extensions of multilevel models that can assess whether the relationship between a predictor and outcome becomes larger or smaller over time. If we see the predicted patterns of change on the “post” item “How useful was the message?,”

we will take that as full support for this hypothesis. If we see it only on other outcome measures (self-efficacy, craving, mood), we will take that as partial support.

Hypothesis 5, distal: Trait predictors of responsiveness (although we are not powering the study to assess treatment matching at the person level, we will examine whether trait variables such as personality and preferred coping styles are associated with differential responsiveness to CBT-based versus ACT-based messages).

This will be tested (with data from the JITAI group only) in multilevel models similar to those for hypothesis 1, with the predictors Intervention Type (either CBT or ACT), Trait, and their interaction. Specific predictions to be tested are: (1) high scorers on the baseline “Need for Closure” scale will benefit more from CBT messages than from ACT messages; (2) participants with steep discounting functions on the Monetary-Choice Questionnaire will be initially resistant to ACT.

The NEO personality inventory and our other trait measures offer many potential predictors, and we do not have *a priori* hypothesis for most of them. In reporting results from any of these analysis, we will specify that they were exploratory, and we will state clearly how many analyses we ran.

Hypothesis/analysis 6 (push versus pull: we will also assess, but have no directional predictions about, whether the intervention types that seem to benefit participants most when “pushed” by the app are the same ones that participants choose when subsequently given the opportunity to “pull” interventions).

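### The Hypothesis 5 model averages over the message period, so it cannot test whether steep discounters' resistance to ACT is confined to the start

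*Combined protocol and SAP*

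**What the plan says.** The discounting prediction appears twice. Section E.3, describing the Monetary-Choice Questionnaire, says: "We will administer this at baseline to test whether people with steep discounting functions are initially resistant to ACT". Section I.2, Hypothesis 5, lists it as one of two specific predictions: "participants with steep discounting functions on the Monetary-Choice Questionnaire will be initially resistant to ACT". Neither place defines 'initially' or names an early window.

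One model serves all of Hypothesis 5. It is described as similar to the Hypothesis 1 models, "with the predictors Intervention Type (either CBT or ACT), Trait, and their interaction".

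The Hypothesis 1 text in section I.2 reads: "We will use multilevel random-intercept models (with data from the JITAI group only) to test the hypothesis of a proximal benefit of messages". It adjusts for the pre-message rating. On the predictor it says: "The main independent variable will be message type: active (CBT or ACT) versus none". On the errors it says: "We will use an autoregressive error structure to account for within-person correlations". No study day, week or count of messages enters.

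Effects that change with time are modelled only under Hypothesis 4: "In the JITAI participants, we will test this hypothesis with time-varying effect models (TVEMs"). No trait moderator is named there.

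The Précis lists trait predictors as a secondary outcome. Sections D and I.2 both say that the study is not powered for matching at the person level.

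**The concern.** The discounting prediction has two parts: steep discounters respond worse to ACT than to CBT, and they do so early. The stated model contains the first part only.

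The timing is what makes the prediction distinctive. Hypothesis 4 already expects ACT messages to take several weeks to be found helpful by participants in general, and section J assumes a message effect that starts small and grows over four weeks. Against that background, the discounting prediction adds a trait difference at the start of messaging.

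At stake is the interpretation of one named secondary prediction. A significant interaction would be compatible with resistance at any point in the eight weeks. A null one would be compatible with early resistance that fades or reverses. The Bayes factors that section I.3 plans for nonsignificant hypothesized effects would likewise address the average effect.

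**Working it through.** The documents give no sample size, power or effect size for Hypothesis 5, so there is no figure to reproduce. The main check is textual; the arithmetic is illustrative.

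**1. Does any planned term carry time?** The Hypothesis 5 predictors are listed, and time is not among them. The parent Hypothesis 1 model has message type, the pre rating, a random intercept and autoregressive errors. Autoregressive errors describe how residuals correlate; they do not let an effect change over time. The time-varying model belongs to Hypothesis 4, without a trait. So the answer is no.

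**2. What does the interaction estimate?** Write the Trait x Type effect on day t as δ(t). Without a time term, the coefficient is approximately Σ w(t)δ(t), where w(t) is the share of completed active prompts on day t.

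**3. How much is a fading effect diluted?** Inputs from section J: 56 days, and availability starting at 0.80 and falling quadratically to an average of 0.60. The exact curve is not given, so I assume two with that start and mean: 0.8 - 0.6u² (ending at 0.20) and 0.5 + 0.3(1 - u)² (ending at 0.50), with u = day/55 and days numbered 0 to 55. Let δ(t) = 1 - t/k for t < k, and 0 afterwards.

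| Effect reaches zero by day k | Average / initial, equal data per day | Average / initial, falling availability |
|---|---|---|
| 7 | 7% | 9-10% |
| 14 | 13% | 17-18% |
| 21 | 20% | 24-26% |
| 28 | 26% | 31-34% |

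With equal weights the sum is (k + 1)/2, so the ratio is (k + 1)/(2 x 56); for k = 28, 14.5/56 = 0.259. If the effect is instead constant and then stops after 1, 2 or 4 weeks, the ratio is simply the share of prompts in those weeks: 16-17%, 31-33% or 56-63% under the two curves.

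An effect running linearly from +1 to -1 averages exactly 0 with equal weights. Under the two availability curves, 9-17% of the initial effect remains.

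**4. Can the planned model tell the profiles apart?** Simulation, 500 replicates: 50 participants, 56 days x 4 prompts, availability constant at 0.60 and two-thirds active messages (all from section J). Assumed: CBT:ACT 1:1, within-person SD 1, independent errors, and an initial effect of 0.30 per SD of trait falling to zero by day 28. Each person's type contrast was regressed on trait, without and with a day interaction, as a two-stage stand-in for the multilevel model. The expected average is 0.30 x 0.259 = 0.078.

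| True profile | Planned coefficient | Rejects | Three-way slope (whole period) | Rejects |
|---|---|---|---|---|
| Initial only | -0.077 | 67% | +0.31 | 81% |
| Constant, same mean | -0.079 | 70% | 0.00 | 6% |
| Late only | -0.074 | 66% | -0.30 | 76% |
| Reversing, 0.30 to -0.30 | 0.000 | 7% | +0.60 | 100% |

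The first three rows cannot be told apart by the planned coefficient: the simulation error on a 67% rejection rate is √(0.67 x 0.33/500) = 2.1 percentage points. The rates depend on the assumed effect and SD and are not power figures for this trial.

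**5. What does estimating the effect at the start cost?** With linear time, Var(effect at day 0)/Var(average effect) = 1 + m²/v, where m and v are the mean and variance of prompt day. With equal weights, m = 27.5 and v = (56² - 1)/12 = 261.25, giving 1 + 756.25/261.25 = 3.9. Under the two availability curves the ratio is 3.3 (m = 22.7, v = 220.5) and 3.4 (m = 25.1, v = 264.6).

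**The case against.** The strongest reply is that the planned model answers the general question of Hypothesis 5, whether traits go with differential response to CBT and ACT, and that it answers it validly. That stands. It can also be said that 'similar to' Hypothesis 1 leaves latitude and that a time-varying model is already in the plan. The latitude is thin: Hypothesis 1 has no time term, and the Hypothesis 5 predictors are spelled out. Extending the time-varying model to a trait is easy, but the plan does not say that it will be done.

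Three stronger readings are tempting, and the documents do not support them.

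- A reader might infer that the model would miss any early effect that fades. In step 4 it still rejected in 67% of runs for an effect gone by day 28; only the reversing profile fell to about the nominal 5%.
- A reader might infer that either result would be misreported. Hypotheses 1, 2 and 4 carry rules for what counts as support, but Hypothesis 5 carries none, and nothing says that an average interaction will be presented as initial resistance.
- A reader might square the dilution fraction and infer that the planned test needs many times more data. That compares it with a constant full-size effect, which is not the prediction, and equal weekly weights ignore the falling availability in section J.

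**Conclusion.** The point holds as a mismatch between one named prediction and its model. The Hypothesis 5 analysis tests average differential response. It cannot test the word 'initially', because initial, constant and late resistance with the same mean give the same coefficient. That conclusion rests on the text and not on any assumed effect size.

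Dilution is real, but its size depends on how fast the effect fades and on how prompts are spread. For a linear fade complete within one to four weeks, about 7% to 34% of the initial effect remains across the weightings considered. Complete cancellation requires a reversal that balances under the actual distribution of prompts.

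Severity is minor. Hypothesis 5 is secondary and declared unpowered, and no sample size or primary conclusion depends on this prediction.

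**What to change.** Before the data are analysed, define 'initially', for example as the effect at the start of JITAI messaging. For the discounting prediction, choose one of these:

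- Add time since JITAI start, or the cumulative number of ACT messages, with all lower-order terms and Trait x Intervention Type x Time. Report Trait x Type at the start of messaging, and use the three-way term to test whether it fades.
- Extend the time-varying effect model already planned for Hypothesis 4 with a Trait x Type coefficient.
- Delete 'initially' in sections E.3 and I.2, and report the result as an average effect only.

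The first two need no new data, provided that each prompt's study day is kept. They have two costs. The start-of-period estimate is less precise, with about 3.3 to 3.9 times the variance of the average effect under linear time, in an analysis that is already unpowered. Early-versus-late contrasts also overlap the Deep Dive lessons, which run for the first 16 nights and up to 21 if nights are missed (section E.3). A change over time may therefore partly reflect that teaching, and the report should say so. A split at two weeks would fall inside that period.

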Primary outcome measures: (1) Proximal effects of CBT and ACT messages in the JITAI group: decreases over 20-minute intervals in craving and negative mood, with increases in self-efficacy; (2) strategy-situation fit in the JITAI group; (3) group differences in distal effects of treatment (week 11 versus week 2) in terms of self-efficacy and coping flexibility.

Secondary outcome measures: (1) Trait predictors of differential responses to CBT and ACT, in the JITAI group; (2) group differences in frequency of opioid-positive urine over time; (3) time courses of responsiveness to ACT vs. CBT, in the JITAI group; (4) whether the intervention types that benefit participants most when “pushed” by the app are the same ones participants choose when subsequently given the opportunity to “pull” interventions.

B. Table of Contents

A. Précis.....	2
B. Table of Contents.....	4
C. Background.....	5
1. From mobile assessment to mobile treatment: a microrandomization approach	5
2. Momentary interventions to be tested in the first arm of this protocol.....	7
3. Two ways to deliver a momentary intervention: push versus pull.....	9
4. Rationale for a multiple-arm protocol.....	10
D. Study objectives	10
E. Study design and methods	11
1. Overview of arm 1.....	11
2. Arm 1, Phase 1: Formative interviews.....	12
3. Arm 1, Phase 2: Clinical trial with microrandomization.....	12
F. Inclusion and exclusion criteria	24
1. Inclusion criteria.....	24
2. Exclusion criteria.....	24
G. Clinical and laboratory methods	25
H. Collection and storage of human specimens or data.....	30
I. Statistical analysis.....	31
1. Outcome measures.....	31
2. Analysis of study outcomes	31
3. Criteria for statistical significance.....	34
J. Required sample size	35
K. Plans for enrollment at multiple sites.....	36
L. Human-subjects protection plan	36
1. Rationale for subject selection based on gender/ethnic/race categories at risk.....	37
2. Recruitment plan	37
3. Justification for exclusion of vulnerable populations	38
4. Evaluation of risks/discomforts and benefits ratio	39
5. Subject monitoring	43
6. Conflicts of interest.....	44
M. Protection of participants' privacy and confidentiality	45
N. Study agents/interventions.....	45
O. Plan for reporting unanticipated problems and adverse events.....	45
P. Data and safety monitoring	45
Q. Clinical monitoring plan.....	46
R. Data/records management	46
1. Quality assurance.....	46
2. Relationship to other protocols	47
3. Data-sharing description.....	47

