For us, however, the choice is dictated by our use of a microrandomized design. The developers of microrandomization (Klasnja et al., 2015) are explicit about this: “Microrandomized trials are not suitable for testing of intervention components that are made available to individuals but which individuals access at will. If a researcher wants to microrandomize a pull intervention component (e.g., graphs for providing feedback on a health behavior), that component first needs to be converted into a push intervention (e.g., a notification to access the graphs).” To keep things as consistent across participants as possible, we will start our clinical trial with a 7-week period of pure “push” interventions, with their content microrandomized. This period will also include a conventional between-groups form of randomization such that one group receives only EMA assessments, with no active mobile intervention. We are including this between-groups variable because microrandomization would allow for assessment only of immediate, context-dependent outcomes, not conventionally assessed overall outcomes. We want to examine both.

Immediately after 7 weeks of pure “push” intervention, the app will allow participants to start “pulling” interventions for another week. We expect this to increase participants’ satisfaction with the app, and we will use it to address additional issues, such as whether participants consistently pull the interventions that appeared to work best for them when pushed. Research in smokers suggests that app users do not always choose the craving-reduction techniques that are objectively associated with the largest benefits (Heffner et al., 2015). One question we want to address in this protocol is when the user knows best and when the system knows best.

4. Rationale for a multiple-arm protocol

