6. We will also assess (but have no directional predictions about) whether the intervention types that seem to benefit participants most when “pushed” by the app are the same ones that participants choose when subsequently given the opportunity to “pull” interventions.

E. Study design and methods

In this section of the protocol, we describe the main experimental aspects of the protocol. We defer description of more routine activities to section G, “Clinical and Laboratory Methods.”

1. Overview of arm 1

This arm of the protocol will consist of a formative-interview phase and a subsequent clinical trial, both to be conducted at the NIDA IRP. Participants may enroll in one or both phases. The interview phase will require only 3 to 4.5 hours from each participant. The clinical trial, which will start after we analyze all the interview information, will last up to 11 weeks per participant (plus a 5-week optional buprenorphine taper for participants we treat here).

Information from the interviews will probably lead to adjustments in the procedures for the clinical trial, but we are laying out a general plan here.

2. Arm 1, Phase 1: Formative interviews

We will conduct interviews with up to 35 people who use opioids (with the goal of getting usable data from 30) who express interest in using a mobile treatment app. Some of them are likely to be current or past participants in other Archway studies (some may be receiving office-based buprenorphine treatment from our clinic; others will be in treatment elsewhere), but others may be enrolled by word of mouth.

In the first part of the interview, to be conducted by a team member with counseling experience, we will ask interviewees about day-to-day challenges that arise as they try to adhere to their treatment goals, and what might be useful in moments when they are tempted to lapse. The approach is purposefully open-ended because we do not want our prior assumptions about lapse to preclude our gathering of important information about preventing it. Interviewees will not be encouraged to reexperience stress or craving, and if they do, they will not be sent home until they have had time to relax.

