For each participant in the JITAI group, we will use multilevel models with person-specific slopes to quantify the relative overall effectiveness of CBT vs. ACT messages during the “push” weeks, in terms of proximal changes craving, self-efficacy, and/or mood. We will then calculate the participant’s relative overall preference for CBT vs. ACT content during the “pull” week. These can be straightforwardly shown in a scatterplot with an accompanying bivariate correlation coefficient.

3. Criteria for statistical significance

The criterion for statistical significance will be set at $p \leq 0.05$, two-tailed. For hypothesized effects that do not reach statistical significance, we will calculate Bayes factors (Dienes, 2014), which help determine whether “nonsignificant” findings favor the null or the alternative hypothesis or whether they should be considered inconclusive.

J. Required sample size

For the formative-interview phase, we anticipate that 30 interviewees will be sufficient to give us feedback on our prototype materials and app interface. We may revisit this if we find that responses are highly variable across interviewees. We expect that most people who agree to be interviewed will provide usable information, so we are setting out enrollment ceiling at 35.

For the microrandomized trial, which is longer and more demanding, we expect a higher rate of dropout. We will enroll up to 150 participants to reach a target of 85 (50 JITAI, 35 EMA control) who complete the week-eleven outcome assessment. The calculations that led us to that total are as follows.

For hypothesis 1 (the proximal main effect of messaging in the microrandomized trial), we used a power-and-sample-size calculator <<https://pengliao.shinyapps.io/mrt-calculator/>> developed specifically for microrandomized studies (Liao et al., 2016). This calculation applies specifically to the JITAI group, not the EMA control group. As Liao et al. (2016) point out, there is very little precedent for determining what a proximal effect size should look like, but small studies with microrandomized designs can often detect seemingly small effects, on the order of $d = .15$. We decided that the most important consideration was to set our beta level high (.90, rather than the conventional .80), and we started by entering the following assumptions:

Days of study: 56 [eight weeks of “push” intervention].

Number of decision time points per day: 4.

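### Analysis 6 (push versus pull): the only planned number, a between-person correlation, does not show whether participants pull the type that worked better for them; agreement figures should be reported beside it

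*Combined protocol and SAP*

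**What the plan says.** The question appears in four places. The Précis, under secondary outcome (4), asks "whether the intervention types that benefit participants most when “pushed” by the app are the same ones participants choose" when they can pull. Section C.3 puts it at the level of the individual: "whether participants consistently pull the interventions that appeared to work best for them when pushed". Section D, item 6, says "We will also assess (but have no directional predictions about) whether the intervention types" match in this way, and Section I.2 repeats the question under Hypothesis/analysis 6.

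The method is at the end of Section I.2. The plan fits "multilevel models with person-specific slopes to quantify the relative overall effectiveness of CBT vs. ACT messages during the" push weeks, computes each participant's relative preference for CBT or ACT content in the pull week, and concludes: "These can be straightforwardly shown in a scatterplot with an accompanying bivariate correlation coefficient". No other summary is named. There is no share of pulls matching the better type, no count of concordant participants, and no reference line on the plot. Unlike hypotheses 1, 2 and 4, analysis 6 has no rule for what would count as support.

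**The concern.** The question is about a match within each person: is the better type the chosen type? The coefficient addresses a different question across people: do those who gain relatively more from CBT also pull relatively more CBT? The two answers can part company when most participants benefit more from the same type. If nearly everyone does better with ACT and mostly pulls ACT, agreement is high, yet the correlation can be near zero. If nearly everyone does better with ACT and mostly pulls CBT, the coefficient can look the same.

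Section C.3 wants this analysis to help show when the user's judgement is to be trusted and when the app's is. A reader given only the coefficient could not always tell those cases apart.

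**Working it through.** Section J gives no power, effect size or sample size for analysis 6, so there is no figure of the plan's own to reproduce.

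**1. Algebra.** Let E be a participant's CBT-minus-ACT benefit and P the CBT share of that participant's pulls. Then r = Σ(E − mean E)(P − mean P) / √[Σ(E − mean E)² · Σ(P − mean P)²]. Adding a constant to E or P leaves r unchanged, so r carries no information on whether E lies above zero or P above 50%. Take five participants with E = 1, 2, 3, 4, 5:

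- P = 0.90, 0.85, 0.80, 0.75, 0.70: everyone mostly pulls the better type, and r = −1.0.
- P = 0.10, 0.15, 0.20, 0.25, 0.30: nobody does, and r = +1.0.

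**2. Simulation with pull counts.** From the documents: 50 JITAI participants, average availability 0.60 and two thirds of messages active (Section J); four prompts a day and seven push weeks, or 49 days (Section E.3); two-tailed 0.05 (Section I.3). Messages per type: 49 × 4 × 0.60 × 2/3 ÷ 2 = 39.2, about 39. The standard error of one person's CBT-ACT difference, in residual-SD units, is √(2/39) = 0.226.

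Assumed, not in the documents: normally distributed true benefit differences, empirical-Bayes shrinkage of the estimated slopes, 10 pulls per participant (5 and 20 give the same picture), and Beta scatter between people (concentration 8). There were 4,000 trials per case.

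| True benefit (mean, SD of the difference) | Pulls of the truly better type | Correlation significant | Same, error-free slopes | Matched share significant against 50% |
|---|---|---|---|---|
| Even split (0, 0.16) | 75% | 76% | about 100% | 52% |
| 80% better on one type | 75% | 54% | 96% | 96% |
| 90% better on one type | 75% | 30% | 72% | 99.9% |
| Nearly all better on one type (0.15, 0.05) | 75% | 5% | 6% | about 100% |
| Same, choices reversed | 25% | 5% | not needed | about 100%, below 50% |
| Nearly all (0.30, 0.15), choice rising with benefit | about 30% | 65%, positive | 99.8% | about 100%, below 50% |

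Rows 4 and 5 are opposite answers with the same coefficient behaviour. The error-free column shows that noise in the slopes is not the cause.

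**3. A second data model.** Here E and P are bivariate normal, the SD of the pull share is 0.15 and N = 50. Agreement is the share of participants whose mostly pulled type is their better type. With p the share better on CBT and q the share mostly pulling CBT, agreement from the margins alone is pq + (1 − p)(1 − q).

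| p, q, within-sample correlation | Median r | Correlation significant | Agreement | From margins alone |
|---|---|---|---|---|
| 0.5, 0.5, +0.6 | 0.61 | 99.8% positive | 70% | 0.25 + 0.25 = 50% |
| 0.9, 0.9, 0 | 0.00 | about 5% | 82% | 0.81 + 0.01 = 82% |
| 0.9, 0.9, −0.4 | −0.40 | 84% negative | 80% | 82% |
| 0.9, 0.1, +0.6 | 0.60 | 99.7% positive | 20% | 0.09 + 0.09 = 18% |

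The level of agreement and its margin-expected value answer different questions, and both are needed.

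**4. Would a test of the matched share against 50% be better?** Using the model of step 2, let choice be unrelated to benefit but let one type be liked more overall. The margin-expected share uses the same formula, with p the share better on ACT and q the mean ACT pull share.

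| p, q | Expected share | Test against 50% rejects | Correlation rejects |
|---|---|---|---|
| 0.5, 0.65 | 0.325 + 0.175 = 0.50 | 31% (16% match, 15% mismatch) | 5% |
| 0.8, 0.65 | 0.52 + 0.07 = 0.59 | 90%, as a match | 4.5% |
| 0.8, 0.35 | 0.28 + 0.13 = 0.41 | 90%, as a mismatch | 5% |

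In the first row the expected share is 0.50 only on average. In a single trial the estimated labels rarely split evenly, so the test rejects in both directions. It holds its level (4.9%) only when overall preference is also 50-50.

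**The case against.** A reader might infer that the correlation is simply the wrong analysis and should give way to a test of the matched share against 50%. The documents do not support that, for four reasons.

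- The person-specific slopes and preference scores suit a legitimate question, whether relative benefit tracks relative choice. The correlation answers it and is protected from a preference shared by everyone.
- Such a shared preference is plausible. Section D, hypothesis 4, expects CBT messages to be rated helpful sooner because they are more direct. Step 4 shows that the 50% test would then report a general liking as knowing, or not knowing, what works.
- Nothing in the documents says that one type will win for nearly everyone. The premise is fit to the situation, with controllability assumed to split roughly 50-50 (Section J). With evenly split benefit, the correlation is the more powerful of the two (76% against 52%).
- The most striking case in step 2 assumes a CBT-ACT difference of 0.30, twice the average effect of 0.15 that Section J plans for any message against none. With mean 0.15 and SD 0.05, the misleading positive result appears in 14% of trials, not 65%.

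It is also fair to say that the planned scatterplot carries part of the missing information, since each point has a sign and a side. In addition, where nearly everyone shares one better type the matched share adds little at person level: with mean 0.15 and SD 0.05, shrinkage labels 99.4% of participants alike, so the share is almost the overall pull share.

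What stands is narrower. The only number planned does not measure the match that the protocol asks about, and the plot has no reference lines from which to read it.

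**Conclusion.** The point holds as a reporting gap of minor severity. That the coefficient ignores which type was better and which was chosen more is algebra and rests on no assumption. How often this would mislead depends on how benefit is distributed across participants, which the documents do not give: little if benefit is evenly split, a great deal if most participants share one better type. The simulated percentages rest on the assumed distributions and pull counts and illustrate the range; they do not predict this trial. No primary or powered analysis is affected, and the lack of a predicted direction makes it more useful to show plainly which way the match went.

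**What to change.** In Section I.2, under Hypothesis/analysis 6, keep the correlation and describe it as the test of whether people with a larger relative benefit from one type choose that type more. Beside it, report:

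- (a) the mean share of pulls that match each participant's better type, as estimated from the push weeks, with a 95% CI;
- (b) both margins: the share of participants better on each type, and the overall CBT/ACT pull share;
- (c) the agreement expected from those margins alone, pq + (1 − p)(1 − q), computed from the same estimated labels;
- (d) the planned scatterplot with lines at zero benefit difference and 50% preference, and the count in each quadrant.

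Read (a) against (c), and do not make the test of (a) against 50% the main statistic. The cost is a paragraph of wording and a few descriptive figures from data already planned. The limitation to state is that the matched share is pulled toward 50% when a participant's better type is misclassified.
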